2.2. Study Design

This is a phase 2 randomized, 3 arm (3 active doses of Reciferecept), parallel group dose-finding study of safety, tolerability, PK and efficacy.

The study will enroll approximately 54 children with achondroplasia aged 2-10 years (inclusive) who will be enrolled and randomized to receive one of three doses of reciferecept (1 mg/kg once-weekly, 2 mg/kg twice-weekly or 1.5 mg/kg once-daily, n=18 per dose) such that at least 15 participants per dose are evaluable. **CCI**

All participants will receive reciferecept for 12 months.

All participants who complete the study and in the opinion of the investigator, continue to have a positive risk:benefit profile, will be offered to enroll into an open-label extension (OLE) study. Participants will continue to receive reciferecept at the dose previously received in this phase 2 study or at the therapeutic dose once this is identified.

Enrollment will follow an age and dose-staggered approach (descending age and ascending dose) with review of safety and PK data by the study team before progression to the next enrollment block (see **Figure 1**). If certain pre-defined safety signals occur then a meeting of the eDMC will be convened to make a decision on progression of enrollment. The PK data collected in block A will be used in the PopPK model (developed using healthy adult data) to confirm the dosing for younger children (ie, ≥ 2 to < 6 years and 0- < 2 years).

[figure not shown]
An interim analysis is planned when at least 15 participants per dose aged ≥ 2 to < 11 years have received 6 months of treatment with reciferecept. eDMC will review safety, PK and efficacy data to confirm ongoing positive benefit:risk in participants.

Progression to the next enrollment block will be controlled by study team review of safety and PK data in the following manner:

Block A to B	Review after all block A participants (n=6) have completed D29
Block B to C	Review once all 2-6y participants (n=6) and 3 high dose 6-10y participants have completed D29
Block C to D	Review once all 0-2y participants (n=6) and 3 high dose 2-6y participants have completed D29

The study design schema is described in **Figure 1**.

Figure 1. Study Design

Note: This is an example of additional explanatory information for the figure.

3. ENDPOINTS AND BASELINE VARIABLES: DEFINITIONS AND CONVENTIONS

3.1. Primary Endpoint(s)

Safety

Safety and tolerability of reciferecept as assessed through frequency and severity of AEs/SAEs.

Efficacy

Increase in height growth above expected in reference population [Merker et al, 2018].

3.1.1. PK Cohort

Pharmacokinetic

The pharmacokinetic parameters following single dose administration will be derived from the concentration-time profile as follows:

Parameter	Definition	Method of Determination
AUC _{inf}	Area under the serum concentration time profile from time 0 extrapolated to infinite time.	AUC _{last} + (C _{last} * / k _{el}), Where C _{last} * is the predicted serum concentration at the last quantifiable time point estimated from the loglinear regression analysis.
AUC ₁₆₈	Area under the serum concentration-time profile from 0 to 168 hours.	Linear/Log trapezoidal method.
AUC ₃₆₀	Area under the serum concentration-time profile from 0 to 360 hours.	Linear/Log trapezoidal method.
C _{max}	Maximum serum concentration.	Observed directly from data.
T _{max}	Time for C _{max} .	Observed directly from data as time of first occurrence.
t _{1/2}	Terminal elimination half-life.	Log _e (2)/k _{el} , where k _{el} is the terminal phase rate constant calculated by a linear regression of the loglinear concentration time curve. Only those data points judged to describe the terminal loglinear decline will be used in the regression.

Actual PK sampling times will be used in the derivation of PK parameters.

3.2. Secondary Endpoint(s)

Safety

- Change from baseline in safety labs, vital signs, physical examination.
- Rate of anti-drug antibodies.

Efficacy

- Sitting height/standing height ratio.
- Arm span to height/length difference.
- Knee height:lower segment ratio.
- Occipito-frontal circumference.
- Ratio of occipito-frontal distance to occipito-mid-face measurements.
- z-score of the above proportionality and skull morphology where achondroplasia reference datasets exist (occipito-frontal circumference, arm span, sitting height).
- Fixed flexion angles at elbow.
- Polysomnography parameters in those with pre-existing sleep-disordered breathing at the time of enrollment.
- Body mass index (BMI).
- Waist:chest circumference ratio.
- Change from baseline in CHAQ component and index scores, QoLISSY Brief total score.

Pharmacokinetic

Population PK characterization in children aged >2 to <11 years old with achondroplasia. Clearance (CL/F) and other PK parameters of reciferecept to assess exposures in different age group.

CCI

20

3.4. Baseline Variables

The following baseline variables will be summarized for each treatment group. Details of summary analyses are described in [Section 6.5.1](#).

Demographic characteristics:

- Baseline age
- Gender (female vs. male);
- Race (white, black, Asian, other);
- Baseline body weight;
- Baseline height (cm);
- Baseline Body Mass.

The baseline data measured at Day 1 are:

- Vital signs
- Physical Examinations

The following variables are to have their baseline value defined as latest screening result relative to Day 1:

- Medical history & demography, Height/Weight.
- Neurological Examinations
- Vital Signs/Physical Examinations with missing Day 1 values

Where Day 1 and/or screening result is missing, baseline data will be defined as the latest result from C4181001 prior to screening, where available.

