2.1. Study Objectives, Endpoints, and Estimands

Objectives	Estimands	Endpoints
Primary:	Primary:	Primary:

Evaluate the safety and tolerability of recifercept doses and dosing regimes in participants aged ≥ 2 to < 11 years with achondroplasia.To assess efficacy of recifercept to increase height growth in children with achondroplasia.	
N/A
 
The primary efficacy estimand is intended to provide a population level estimate of the effect of recifercept on a continuous endpoint. 
Population-level summary: ratio between participants in the trial and a reference population [Merker et al, 2018]¹ in growth of height at 12 month; ratio between treated and reference population is observed change-from-baseline of treated participants standardized by reference participant given age and gender.
	
Safety and tolerability of recifercept as assessed through frequency and severity of AEs/SAEs.
 
Increase in height growth above expected in reference population [Merker et al, 2018]¹
Secondary:	Secondary:	Secondary:

To evaluate the pharmacokinetics (PK) of recifercept in children aged ≥ 2 to < 11 years old with achondroplasia.To assess efficacy of recifercept to improve achondroplasia-related complications.		
Population PK characterization in children aged ≥ 2 to < 11 years old with achondroplasia. Clearance (CL/F) and other PK parameters of recifercept to assess exposures in different age group.
 
Sitting height/standing height ratio.Arm span to height/length difference.Knee height:lower segment ratio.Occipito-frontal circumference.

Objectives	Estimands	Endpoints
		
 Ratio of occipito-frontal distance to occipito-mid-face measurements. z-score of the above proportionality and skull morphology where achondroplasia reference datasets exist (occipito-frontal circumference, arm span, sitting height). Fixed flexion angles at elbow. Polysomnography parameters in those with pre-existing sleep-disordered breathing at the time of enrollment. Body mass index (BMI). Waist:chest circumference ratio. Change from baseline in CHAQ component and index scores, QoLISSY Brief total score.

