5.3. Methods to Manage Missing Data

In general, for descriptive statistics missing values will not be imputed. In addition, for safety endpoints missing values will not be imputed. Other methods for handling missing values are discussed below. Missing data methods for baseline values are discussed in [Section 3.4](#).

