Appendix 2.2. Endpoint Derivations

Height Growth

The primary efficacy endpoint is H defined by the following:

$$H_{ijkl} = \frac{Y_{ijkl} - Y_{i0kl}}{Z_{jl} - Z_{0l}},$$

where Y_{ijkl} is the observed standing height for the i th subject, at month j on dose k with gender factor l ($j=0$ denotes baseline measurement) and Z_{jl} is the mean expected standing height based on Merker for subject i 's age.

Mean expected standing height from Merker is sorted by 6 months up to age 4, while means expected values for children > 4 years are sorted per annum. Linear interpolation will be employed to calculate mean expected values so that mean standing height are sorted at 6 month intervals for children > 4 years. SAS code for the linear interpolation calculation will be provided in Appendix 4.

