Appendix 2.3. Definition of Protocol Deviations That Relate to Statistical Analyses/Populations

Appendix 3. Data Set Descriptions

Appendix 4. Statistical Methodology Details

Linear Interpolation

Linear interpolation will be employed to provide mean expected standing height values at 6 month interval for children $>$ age 4. The SAS code is as follows:

```
proc expand data=mydata out=LinInterp;
  convert exp_mean=linear / method=join;
  id age;
run;
```

MMRM

MMRM will be used for height growth and arm span-height difference. The SAS code is as follows:

```
proc mixed data=mydata;
  class dose gender month;
  model height = dose month gender age/s;
  random int month / type=un sub=subject;
  lsmean dose;
run;
```

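### SAP 3.4 takes baseline height from screening, or from C4181001, instead of the scheduled Day 1 anthropometry, and the SAP does not say whether expected growth runs over actual dates or nominal months

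*SAP*

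**What the plan says.** SAP 3.4 has two lists of baseline variables. The Day 1 list holds only vital signs and physical examinations. The other opens with "The following variables are to have their baseline value defined as latest screening result relative to Day 1" and includes "Medical history & demography, Height/Weight". A fallback follows: "Where Day 1 and/or screening result is missing, baseline data will be defined as the latest result from C4181001 prior to screening".

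The section is introduced as a rule for summaries ("The following baseline variables will be summarized for each treatment group"), but SAP 5.3 sends the reader back to it for the analyses: "Missing data methods for baseline values are discussed in" Section 3.4.

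The primary variable (SAP 2.1.1) is observed change from baseline in standing height divided by expected change. SAP 2.1 describes it as "observed change-from-baseline of treated participants standardized by reference participant given age and gender". In Appendix 2.2, j=0 "denotes baseline measurement", with no visit named, and the reference mean is taken for the child's age, with no date given. SAP 6.1.1.1 and protocol 9.1.1, 9.2 and 9.4.2 do not name a baseline visit either. Appendix 4 adds: "Linear interpolation will be employed to provide mean expected standing height values at 6 month interval for children" older than 4; Appendix 2.2 says the younger ages are already in 6-month steps.

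In the protocol's Schedule of Activities, the anthropometry row is marked at Day 1 and Months 3, 6, 9 and 12. The screening cell is empty.

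**The concern.** The only written rule for baseline height passes over the one pre-dose measurement scheduled for the endpoint. Read literally, it also gives a C4181001 height to a child who has a Day 1 height but no screening height.

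The primary test compares each dose with external reference growth, so no concurrent control arm shares an offset in baseline. Growth between the earlier height and Day 1 enters the numerator. Its effect depends on the denominator. If expected growth starts on the same date, the untreated days only dilute the effect. If expected growth is a fixed 12 months, they count as drug effect. The SAP does not say which applies, so the size and direction of the offset would be settled at analysis.

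**Working it through.** **Inputs**
- Screening window Day -14 to -1 and Month 12 at D365 (Schedule of Activities). Day 1 to D365 is 364 days, and the longest screening lag is 14 days.
- A C4181001 height is required within 3 months before enrolment (protocol 5.1, criterion 3), taken as 91 days. The protocol synopsis dates enrolment at consent, so screening can add 14 days: 91 + 14 = 105 days.
- 15 evaluable children per dose, one-sided familywise error 0.05, three comparisons, variability .15, target 50% above reference (protocol 9.2). The scale of .15 is not stated. It is read as an SD of the ratio (0.15) and, alternatively, as a variance (SD √0.15 = 0.387).
- SAP Month 12 window Day 346 to 366 (Appendix 2.1).

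**The plan's own figures.** 0.05/3 = 0.0167, which rounds to the stated 0.017. A one-sample t test of the mean ratio against 1, with difference 0.5 and n = 15, has power of about 1.00 (SD 0.15) or 0.993 (SD 0.387). The stated power of over 90% holds and is not in dispute.

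**Reading A: expected growth dated from the same measurement as baseline height.** With steady growth, the null ratio is (364 + lag)/(364 + lag) = 1.00. A true 1.50 becomes (1.5 × 364 + lag)/(364 + lag):
- 7 days: 553/371 = 1.491
- 14 days: 560/378 = 1.481
- 91 days: 637/455 = 1.400
- 105 days: 651/469 = 1.388

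At 1.481, per-dose power is about 1.00 (SD 0.15) or 0.989 (SD 0.387).

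**Reading B: expected growth fixed at a nominal 12 months.** At D365 with no drug effect, the ratio rises by lag/364:
- 7 days: 0.019
- 14 days: 0.038
- 91 days: 0.250
- 105 days: 0.288

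The last two apply to an individual child on the fallback. At Month 6 (182 days) the same lag counts double: 14/182 = 0.077.

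Per-dose one-sided error under Reading B, by the screening route (nominal 1.7%; n = 15; one-sample t test in place of the MMRM; child mean = (visit day − 1 + lag)/364; 1,000,000 simulated trials per cell):

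| Lag and SD | All visits at D365 | Visits uniform, Day 351-366 | Visits uniform, Day 346-366 |
|---|---|---|---|
| 1-14 days, SD 0.15 | 5.1% | 2.0% | 1.3% |
| All 14 days, SD 0.15 | 11.3% | 5.1% | 3.6% |
| 1-14 days, SD 0.387 | 2.6% | 1.8% | 1.5% |
| All 14 days, SD 0.387 | 3.8% | 2.6% | 2.2% |

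The D365 cells with all lags at 14 days agree with the noncentral t distribution (0.113 and 0.038). Early Month 12 visits shorten the observed interval and can cancel the lag. With lags of 1-14 days and visits spread over the SAP window, the error falls below nominal.

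**The case against.** The other side has good points.

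- **Age is partly dated.** A reader might infer that nothing in the SAP dates the age behind expected growth. That goes too far. SAP 3.4 lists baseline age as a demographic characteristic and puts demography in the same bullet as height, so on the literal reading both carry the screening date. Appendix 2.2 indexes expected height by 0 and j, which implies age at baseline and at month j. The analysis also needs expected growth at Months 3 and 9, which a bare 6-month grid cannot supply without finer interpolation. This favours Reading A, but no section says whether age at month j is actual or nominal.
- **The fallback should be rare.** A reader might infer from the empty screening cell that most children would get a C4181001 height. Protocol 8.2.1 includes height in the physical examination, to the same measurement manual, and that examination is scheduled at screening. A screening height should normally exist.
- **Day 1 was probably meant.** Section 3.4 is framed as summaries and omits arm span, sitting height and head circumference. The fallback sentence mentions Day 1. Protocol 8.1.1 has waist and chest measured at baseline, and 8.2.6 separates the baseline visit from screening. This shows likely intent. It does not replace a rule that says otherwise and to which SAP 5.3 refers.
- **Inflated error is not established.** A reader might infer that the primary test is biased towards success. The 11.3% needs Reading B, SD 0.15, every child at 14 days and every visit at D365. Reading A gives no inflation.
- **The visit window is a separate matter.** Under Reading B, even a Day 1 baseline gives a mean null ratio of 0.975 when visits spread over Day 346-366. That comes from the window, not from SAP 3.4, and adds no weight here.

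**Conclusion.** The point holds as a minor, low-cost correction. SAP 3.4 directs baseline height away from the scheduled Day 1 measurement, no section names Day 1 height as j=0, and the choice between actual dates and nominal months for expected growth is not written down.

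By the screening route the consequence is small against the 0.5 effect sought: dilution to 1.48-1.49 if the dates match, or a rise in the null ratio of at most 0.038 at D365 if they do not. A fallback child could be off by more (about 1.39-1.40 in place of 1.50, or up to 0.25-0.29 above the null), but few such children are expected and their number is unknown. Net error inflation is possible and not certain.

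These sizes assume steady growth over the interval and 3 months taken as 91 days. The error rates also assume a t test in place of the MMRM, a scale for .15, and distributions of lag and visit day that the documents do not give.

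**What to change.** In SAP 3.4 and Appendix 2.2:

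1. Define baseline for height and the other anthropometric endpoints as the Day 1 pre-dose anthropometry. Use a screening height, and then a C4181001 height, only if Day 1 is missing.
2. Compute expected growth from the child's age on the actual dates of the baseline and visit measurements, interpolating between the 6-month reference points. State how age is set where only month and year of birth are recorded (protocol section 8 allows this as a minimum).
3. Report the number of children whose baseline is not Day 1. A sensitivity run without any children on a C4181001 baseline is optional.

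The cost is wording in two places of the SAP and one count. The Day 1 measurement is already scheduled, and the sample size and power statement do not change. Dating expected growth to actual visits also removes the separate visit-window offset.

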3.5. Safety Endpoints

- laboratory data
- vital signs data
- physical examination

3.5.1. Adverse Events

Any events occurring following start of treatment or increasing in severity will be counted as treatment emergent.

Events that occur in a non-treatment period (for example, washout or follow-up) will be counted as treatment emergent and attributed to the previous treatment taken.

3.5.2. Laboratory Data

Safety laboratory tests will be performed as described in the protocol.

To determine if there are any clinically significant laboratory abnormalities, the haematological, and blood chemistry safety tests will be assessed against the criteria specified in the sponsor reporting standards. The assessment will take into account whether each subject's baseline test result is within or outside the laboratory reference range for the particular laboratory parameter.

Baseline will be defined as the measurement on Day -1, or the last available pre-dose collection time point (whichever occurs later).

3.5.3. Physical Examination

Physical examination assessments will be performed as described in the protocol. Baseline will be defined as the last pre-dose measurement on Day 1.

4. ANALYSIS SETS (POPULATIONS FOR ANALYSIS)

Data for all participants will be assessed to determine if participants meet the criteria for inclusion in each analysis population prior to unblinding and releasing the database and classifications will be documented per standard operating procedures.

Population	Description
Full Analysis Set (FAS)/Safety	All participants receiving at least one dose of reciferecept. Participants will be analyzed according to the dose they actually received.
Per-Protocol Analysis Set (PPAS)	All participants receiving at least one dose of reciferecept and have complete data at baseline through month 12 and without protocol deviations that were thought to impact the efficacy evaluation during the treatment period. Participants will be analyzed according to the randomized intervention.
PK Concentration set	All participants who received at least one dose of reciferecept and have at least one evaluable concentration.
PK Study Cohort	All participants who received a dose of the reciferecept Phase 2 formulation and a dose of the Phase 3 formulation with at least one evaluable concentration result.

Population	Description
PK Study Cohort Parameter (PKCP)	All participants in the PK cohort who have at least one PK parameter of interest.

5. GENERAL METHODOLOGY AND CONVENTIONS

The final analysis will be performed after all study participants completed treatment and follow-up period, and the CSR will be issued after them.

5.1. Hypotheses and Decision Rules

The null hypothesis for primary efficacy analysis is that observed height growth 12 months post-baseline for children on reciferecept is equal to the expected height growth for the achondroplasia reference population based on Merker (2018). The alternative hypothesis is that observed height growth 12 months post-baseline for children on reciferecept is greater than the expected height growth for the achondroplasia reference population based on Merker (2018).

The Bonferroni correction method is used to control the overall familywise error rate of 0.05 for multiple comparisons. The post-baseline estimate will be considered statistically significant at the 1-sided 0.017 level.

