4. STUDY DESIGN

4.1. Overall Design

This is a phase 2 randomized, 3 arm (3 active doses of Recifercept), parallel group dose- finding study of safety, tolerability, PK and efficacy.

The study will enroll approximately 54 children with achondroplasia aged 2-10 years (inclusive) who will be enrolled and randomized to receive one of three doses of reciferecept (1 mg/kg once-weekly, 2 mg/kg twice-weekly or 1.5 mg/kg once-daily, n=18 per dose) such that approximately 45 participants are evaluable (up to 15 participants per dose). Additionally, **CCI** cohort of approximately 9 children with achondroplasia, ages 3 months to 2 years, will be enrolled later in the study (n=3 per dose). All 63 participants in this part of the study will receive reciferecept for 12 months.

PK Study Cohort:

At selected sites only, an additional PK cohort has been added to evaluate the PK of two reciferecept formulations. A total of 12 children with achondroplasia aged 2- < 11 years will be enrolled in the PK cohort (6 in each treatment sequence). Each participant will receive 2 treatments (3 mg/kg Phase 2 formulation [process 1c] and 3 mg/kg Phase 3 formulation [process 2]) in a randomized manner according to one of two sequences as outlined in [Table 1](#) below. Dose of the cohort could be changed due to emerging safety and efficacy data in the study.

PK samples collected following each dose will be analyzed to evaluate the exposures of two formulations.

Table 1. Treatment Sequence

Sequence	Period 1	Period 2
1 (n = 6)	Phase 2 study (process 1c) Formulation	Phase 3 study (process 2) Formulation
2 (n = 6)	Phase 3 study (process 2) Formulation	Phase 2 study (process 1c) Formulation

All participants who complete the study and in the opinion of the investigator, continue to have a positive risk: benefit profile, will be offered to enroll into an open-label extension (OLE) study. Participants will continue to receive recifercept at the dose previously received in this phase 2 study or at the therapeutic dose once this is identified.

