9.2. Sample Size Determination

Sample size determination is based on the co-primary endpoint of height growth, defined as change from baseline of height at 12 months for participants on drug versus change from baseline of height at 12 months for a reference achondroplasia population. A total of 54 participants randomized to three dose levels in order to obtain 15 participants per dose, assuming a one-sided family-wise error rate of 0.05 with a Bonferroni correction (0.017 after Bonferroni adjustment for 3 comparisons), and inter-participant variability of .15 (estimated from C4181001), there is over 90% power to detect at least one dose providing 50% height growth above reference. No statistical comparison will be made between recifercept doses.

PK Study Cohort:

No formal sample size calculation was performed and 12 participants will be selected empirically to characterize PK, safety and tolerability after single 3 mg/kg dose administration of two formulations.

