2.1.1. Primary Estimand(s)

The primary estimand is defined according to the primary objective and is in alignment with the primary endpoint. It includes the following 4 attributes:

- Population: Patients with achondroplasia, as defined by inclusion/exclusion criteria;
- Variable: Height Growth at 12 months;
- Height Growth = (Observed Change from Baseline in standing height (cm))/(Expected Change from Baseline (cm)[Merker et al, 2018]¹)

- Intercurrent event(s): Withdrawal and all events leading to missing data will be excluded from efficacy analysis and will not have their data imputed;
- Population-level summary: Mean Height growth at 12 months adjusted for age and gender.

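### Testing the three doses by Holm's step-down rule instead of a fixed 0.017 would keep the same familywise error and gain power for the second and later doses only: a cheap improvement, not an error

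*SAP*

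**What the plan says.** SAP 5.1 sets the null hypothesis as growth on recifercept equal to the growth expected from the published reference, and the one-sided alternative as growth above it. It then says "The Bonferroni correction method is used to control the overall familywise error rate of 0.05 for multiple comparisons" and "The post-baseline estimate will be considered statistically significant at the 1-sided 0.017 level". Protocol 9.5 carries the same rule. No step-down procedure appears in either document.

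Protocol 9.2 gives the arithmetic: "assuming a one-sided family-wise error rate of 0.05 with a Bonferroni correction (0.017 after Bonferroni adjustment for 3 comparisons"). It states the size as "A total of 54 participants randomized to three dose levels in order to obtain 15 participants per dose", with "inter-participant variability of .15 (estimated from C4181001"), and concludes that "there is over 90% power to detect at least one dose providing 50% height growth above reference". The synopsis repeats this. No power is stated for showing every effective dose.

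The endpoint is a ratio, "Height Growth = (Observed Change from Baseline in standing height (cm))/(Expected Change from Baseline (cm"), so each test compares a dose mean with 1. Protocol 9.2 and 9.5 rule out tests between doses, so the family is the three dose-versus-reference tests. Protocol 9.4.2 also applies the Bonferroni adjustment to the 95% intervals for the primary endpoint.

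**The concern.** Single-step Bonferroni holds every dose to 0.05/3 even after another dose has already been declared positive. Holm relaxes the threshold to 0.05/2 and then 0.05 as doses are rejected, at the same familywise rate.

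This matters because the trial is dose-finding. The weekly totals are 1, 2 × 2 = 4 and 1.5 × 7 = 10.5 mg/kg. Protocol 4.3 says the doses were chosen to span a wide exposure range and that the efficacious exposure is highly uncertain. Effects may well differ between doses. Since the alternative is any growth above reference, a dose with an effect well below +50% would still count as positive. What is at stake is how many effective doses, and in particular whether the lowest one, the trial can identify.

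**Working it through.** **Inputs.** Familywise one-sided 0.05, three comparisons, 15 evaluable per dose, planning effect 0.50 on the ratio scale, variability 0.15 (all protocol 9.2). The ratio endpoint is from SAP 2.1.1. The documents give no unit for the 0.15; I take it as an SD on the ratio scale and also vary it. Effects below +50% are assumptions, because the documents give none.

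**Alpha.** 0.05/3 = 0.0167, rounded to 0.017 (3 × 0.017 = 0.051, a rounding matter only).

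**The plan's own figure.** One-sample t test on 14 df, noncentrality = effect / (SD/√n).
- At 0.50 and SD 0.15: 0.50 / (0.15/√15) = 12.9. Power for one dose exceeds 99.99%.
- If 0.15 is a variance (SD 0.387): 99.3% for one dose and above 99.99% for at least one of three.
- The stated figure of over 90% therefore holds as a lower bound. The SD would have to reach about 0.52 for one dose, or 0.80 for any of three equally effective doses, before power fell to 90%.

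**Why power for at least one dose cannot change.** Both methods need the smallest p-value to be at or below 0.05/3 before anything is rejected. Only later rejections can differ.

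**Direct calculation at +10%, SD 0.15.** Noncentrality = 0.10 / (0.15/√15) = 2.58.
- Power at 0.05/3 is 0.596. Under Bonferroni with independent arms, all three give 0.596³ = 0.21, and at least one gives 1 − (1 − 0.596)³ = 0.93.
- Power at 0.05 is 0.79. If the other two doses are at +30% and +50%, they are rejected almost always, so Holm tests the lowest dose at 0.05. Its power is 0.79 instead of 0.60.

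**Simulation.** At least 400,000 trials per scenario, 15 per arm, separate one-sample t tests unless marked pooled, both methods applied to the same p-values.

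| True excess per dose | SD | Power for | Bonferroni | Holm |
|---|---|---|---|---|
| +50% each | 0.15 | all three | 100% | 100% |
| +20% each | 0.15 | all three | 98.5% | 99.8% |
| +14% each | 0.15 | all three | 69% | 89% |
| +14% each, pooled variance | 0.15 | all three | 78% | 92% |
| +10% each | 0.15 | all three | 21% | 46% |
| +10% each, pooled variance | 0.15 | all three | 29% | 52% |
| +10, +30, +50% | 0.15 | lowest dose | 60% | 79% |
| 0, +10, +10% | 0.15 | both effective doses | 36% | 45% |
| 0, 0, +10% | 0.15 | the one effective dose | 60% | 60% |
| +50% each | 0.5 | all three | 78% | 94% |

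Power for at least one dose was identical under the two methods in every scenario, for example 93% at +10% each.

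**Error rates.** With no effective dose, familywise error is 0.049 under both. With one null dose and two at +50%, the chance of falsely declaring the null dose effective is 0.017 under Bonferroni and 0.050 under Holm. With one null dose and two at +10%, it is 0.017 and 0.035.

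**The case against.** The best case for leaving the plan alone is that Bonferroni is pre-specified, stated consistently and controls the rate it claims to control. The trial is powered only for at least one dose, and Holm's gain there is exactly zero whatever the inputs. At the planning assumptions there is nothing to gain for all three doses either. All of this stands. A reader might infer that the plan is wrong, underpowered, or wasting power at its own design point. The documents support none of those readings.

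The gains also depend on the pattern assumed. Equal small effects in all three doses show them at their largest. With one null dose the gain is about 9 points, and with two null doses it is negligible. The planned analysis is one model across doses, not three separate t tests. Pooling the variance trims the gain from 25 to 23 points at +10%, and from about 20 to 14 at +14%. These limits reduce the size of the point without removing it.

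The most substantive objection concerns the lowest dose. If the two upper doses work and the lowest does not, Holm triples the chance of calling the lowest dose effective, from 0.017 to 0.050. That cost is real. It stays within the 0.05 familywise rate that the plan chose, so it is a trade-off to disclose and not a loss of control.

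A further objection is that adjusted intervals would no longer match the tests. They do not match now. A Bonferroni-adjusted two-sided 95% interval (protocol 9.4.2) corresponds to 0.05/3/2 = 0.0083 one-sided, and the 95% intervals in SAP 6.1.1.1, where no adjustment is mentioned, correspond to 0.025. Neither is 0.017.

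**Conclusion.** This is an optional improvement in efficiency. The present rule is valid, and the sample size and stated power are unaffected by the choice.

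Holm would help only with the second and later doses, and only if some effects are about +20% or less at SD 0.15, or if the SD is well above 0.15. Under such assumptions the gain runs from about 9 points (one null dose, two at +10%) through 19 points (lowest dose at +10, +30, +50%) to about 25 points (all three at +10%). It is zero at the plan's own inputs and close to zero when only one dose works. The figures rest on reading 0.15 as an SD of the ratio, on 15 evaluable children per dose, on independent arms, and on effect sizes that the documents do not supply. Holm's control of the familywise rate needs none of these assumptions.

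**What to change.** Before the Month 12 data are unblinded and released for analysis, replace the fixed 0.017 rule in SAP 5.1 and protocol 9.5 with Holm's procedure at one-sided familywise 0.05 over the three Month 12 dose-versus-reference tests. Suggested text: *The three one-sided p-values will be ordered; the smallest is compared with 0.05/3, the next with 0.05/2 and the largest with 0.05, stopping at the first that is not significant.*

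Align the Bonferroni wording in the protocol synopsis, 9.2 and 9.4.2. The sample size statement keeps its numbers, because Holm's first step is still 0.05/3. Keep the Bonferroni-adjusted intervals for reporting, and say that they may not match the Holm decision for the second and third dose. State also that the false-positive chance for a null dose can reach 0.050 when the other two doses are effective.

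The cost is a few sentences and a protocol amendment, since both documents require one for a major change to the primary analysis. No further participants are needed.
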